HLA-DR+	Human Leukocyte Antigen-antigen D related
HRPP	Human Research Protection Program
hsCRP	High Sensitivity C-reactive protein
hsTnT	High Sensitivity Troponin
IFN- γ	Interferon-gamma
IHV	Institute of Human Virology
IL-6	Interleukin 6
IRB	Institutional Review Board
MRI	Magnetic Resonance Imaging
MTA	Materials Transfer Agreement
N	Number (typically refers to number of subjects/sample size)
NIH	National Institutes of Health
NK	Natural Killer (cells)
PD-1	Programmed Cell Death Protein 1
PEG-IFN- α	Pegylated interferon-alpha
PWID	People who inject drugs
PI	Principal Investigator
PRO	Patient Reported Outcomes
RNI	Reportable New Information
SAE	Serious Adverse Event/Serious Adverse Experience
SOC	Standard of Care
SOM	School of Medicine
SVR	Sustained Virologic Response
TIM-3	T Cell Immunoglobulin and Mucin Domain 3
TNF- α	Tumor Necrosis Factor alpha
UP	Unanticipated Problem

UPnonAE

Unanticipated Problem that is not an Adverse Event

Protocol Summary

Full Title:	Cardiovascular disease in HIV and Hepatitis C: Risk Outcomes after hepatitis C Eradication
Short Title:	CHROME
Conducted by:	Institute of Human Virology, University of Maryland
Principal Investigator:	[name], DO
Sample Size:	N= 90; 60 on hepatitis C treatment; will consent up to 200 for screening
Study Population:	Adults infected with HIV and/or HCV
Accrual Period:	12 months
Study Design:	This is a pilot, intervention, non-randomized, controlled prospective study. We will enroll 90 patients into 3 groups. Patients with HCV mono-infection (Group 1) or HIV/HCV co-infection (Group 2) will receive therapy with DAAs. Patients with HIV mono-infection (Group 3) will be followed throughout the study and laboratory work and imaging will be obtained.
Study Duration:	Start Date: September 2018 End Date: July 2021
Primary Objective:	Determine the change in cardiovascular risk from baseline to after functional cure of hepatitis C among HCV monoinfected and HIV/HCV-coinfected patients, using high-sensitivity C-reactive protein.
Secondary Objectives:	
1) Determine the difference in change (pre vs. post functional cure) in cardiovascular risk among HCV monoinfected and HIV/HCV coinfecting patients compared to HIV monoinfected patients, using high-sensitivity C-reactive protein.2) Compare the difference in levels of cardiac biomarkers between HCV monoinfected, HIV/HCV coinfecting, and HIV monoinfected patients at baseline.3) Determine the difference in change (pre vs. post functional cure) in cardiac biomarkers among HCV monoinfected and HIV/HCV coinfecting patients, compared to HIV monoinfected patients.
Exploratory Objectives:	
1) Compare the difference in cardiac MRI between HCV monoinfected, HIV/HCV coinfecting, and HIV mono-infected subjects at baseline. MRI parameters that will be assessed

are the native myocardial T1, myocardial T2, and myocardial extracellular volume fraction (to look for myocardial inflammation and small vessel disease). Gadolinium enhancement will be used to look at macroscopic fibrosis.

- 2) Determine the difference in change (pre vs. post functional cure) in cardiac MRI in HCV monoinfected and HIV/HCV coinfect patients, compared to HIV monoinfected patients. MRI parameters that will be assessed are listed in objective 1.
- 3) Determine the relationship between immune markers of activation, cardiac biomarkers, and MRI in HIV positive and negative subjects. MRI parameters that will be assessed are listed in objective 1.
- 4) Compare the difference in levels of cellular and soluble immune markers of activation between HCV monoinfected, HIV/HCV coinfect, and HIV monoinfected subjects at baseline.
- 5) Determine the difference in change (pre vs. post functional cure) in cellular and soluble immune markers of activation HCV monoinfected and HIV/HCV coinfect patients, compared to HIV moninfected patients.

Précis

Among people living with HIV (PLWH), there is a 50% increased risk of acute myocardial infection compared to the general population(1). Although the advent of highly active antiretroviral therapy (HAART) has had several benefits for PLWH, including increased life expectancy(2), the longer life span has also made this population apt to develop comorbidities seen in age-matched individuals without HIV, including cardiovascular disease. In addition, HAART itself is a risk factor for cardiovascular disease (CVD)(3), and persistent inflammation and chronic immune activation caused by HIV and ART results in a proinflammatory state that also increases the risk for cardiovascular disease(4).

Hepatitis C (HCV) is another chronic viral infection with significant morbidity and mortality. The development of directly acting antivirals (DAAs) has dramatically improved the cure rate of HCV treatment. However, besides the effects on the liver, chronic infection with HCV leads to numerous extrahepatic manifestations that are associated with morbidity and mortality, including cardiovascular disease(5, 6). Therefore, patients co-infected with HCV and HIV have a magnified cardiovascular risk than that of the general population (7). If treatment of HCV can lower the risk of CVD among HIV and HCV co-infected patients, then this would provide an indication for early HCV treatment in this population.

As such, we propose a pilot, intervention, non-randomized, controlled prospective study to treat HCV in mono-infected and HIV co-infected individuals and compare cardiovascular risk outcomes to HIV mono-infected controls. This pilot study will demonstrate whether functional cure of HCV reduces myocardial injury and risk of cardiovascular disease.

1 Background Information and Scientific Rationale

1.1 Background Information

Rates of cardiovascular disease (CVD) are over twice as high in HIV-infected individuals compared to matched uninfected controls, with rates anticipated to increase as this population ages(8). Factors contributing to increased risk of CVD in HIV-infected patients remain unclear, but there is considerable evidence suggesting that concurrent viral disease, especially HCV, is an important contributing factor. With the advent of direct acting antivirals (DAA), HCV is now a factor that can be easily eliminated. Hepatitis C (HCV) co-infection occurs in approximately one-third of all patients infected with human immunodeficiency virus (HIV) in the U.S(9). The early treatment of HCV in this population could be an important intervention to reduce the burden of liver disease; thus far, early treatment has been a controversial intervention in patients with no fibrosis given the cost of HCV treatment. Moreover, chronic HCV is an important model for understanding the role of chronic viruses in accelerating inflammation and organ dysfunction in multiple anatomic sites.

While some studies have strongly suggested that hepatitis C (HCV) co-infection is associated with increased rates of CVD in HIV-infected patients, results in all studies have not been consistent. However, several of these larger cohort studies included predominantly Caucasian and male participants in the pre-antiretroviral therapy era(8). Given that HIV, HCV, and atherosclerosis are all associated with chronic inflammation and immune activation, it can be challenging to understand relative disease pathogenesis when found concurrently in individual patients. Identifying predictors of CVD progression from overlapping pathways has the potential to suggest novel preventive and therapeutic intervention strategies to mitigate CVD progression. If HCV confers additional risk for CVD among HIV-infected patients, this would provide further impetus to treat HCV early and aggressively in this population.

Myocardial injury and vascular complications associated with HIV can be differentiated by the use of cardiac MRI. Cardiac MRI is an established modality for the evaluation of myocardial injury and cardiac function(10, 11). Infarcted regions in the myocardium, having undergone scar formation with collagen deposition, have a much slower washout rate of gadolinium-based contrast than healthy myocardium, leading to significantly increased signal intensity on T1-weighted imaging. Therefore, the presence and size of regional myocardial fibrosis due to ischemic heart disease can be accurately assessed with delayed contrast enhancement MRI (12). Unlike computed tomography, with which Hounsfield units can be used as a reference scale for attenuation, with conventional MRI techniques, signal intensity is expressed on an arbitrary scale that differs from one imaging examination to another and therefore is unsuitable for direct signal quantification. Theoretically, diffusely fibrotic myocardium would accumulate contrast in a similar fashion to regional scarring, but calculation of the T1 time is required for its quantification, and is a technique that we have expertise with at the NIH. Measurement of cardiac function is a well described prognostic tool to evaluate myocardial health, and is also an integral component of a complete cardiac MRI conducted at the NIH. This modality may be effective in distinguishing variable myocardial injury between HIV mono-infected and HIV/HCV co-infected individuals. In

fact, a prior study of 18 patients demonstrated worse cardiac function and morphology in HIV/HCV patients who underwent cardiac MRI and spectroscopy for measures of cardiac function, myocardial fibrosis, and steatosis which compared to HIV mono-infected controls(13). However further studies are necessary to reinforce this finding, and elucidate underlying mechanisms of injury.

The objective of this study is to determine the impact of functional cure of HCV (sustained virologic response [SVR]) on cardiovascular risk and progression of CVD in a population of HCV mono-infected and HIV/HCV-coinfected patients compared to HIV mono-infected controls.

1.2 Institutional Overview

Overview of the DC PFAP Hepatitis Program

In 2008, the National Institutes of Health and the DC Department of Health collaborated to establish the DC Partnership for HIV/AIDS Progress (DC PFAP), a partnership for community-based clinical care and research whose aim is to reduce the incidence and prevalence of HIV/AIDS in the District of Columbia. A plan was developed to create a research program to build a sustainable model for urban areas working to reduce the HIV/AIDS crisis. A needs assessment within the area's medical community demonstrated a significant deficit in hepatitis C virus care and treatment. This led to the development of a Hepatitis branch within DC PFAP, rooted in direct subspecialty medical services and clinical research addressing the limitations of standard of care therapy.

The Hepatitis program is currently based at the Institute of Human Virology and operates out of three campuses: (1) clinical partners within Washington DC, (2) National Institutes of Health, Bethesda, MD and (3) University of Maryland Institute of Human Virology, Baltimore, MD. The overarching goals of the programs are to:

- establish improved access to subspecialty care for underinsured patients with HIV
- develop access to HIV- and hepatitis-related research for residents of DC
- expand integrated care for hepatitis C in the community HIV clinics
- provide national leadership in the development and delivery of effective, safe, convenient therapies, initially focusing on HCV

The clinical aspects of the program are set within partner centers in Washington DC and Baltimore City. In the Unity clinic system in Washington DC, we have established relationships with the providers and access to a cohort of patients with HIV and Hepatitis C. In Baltimore City, the Center for Infectious Disease (CID) provides comprehensive care services for a range of infectious diseases, including HIV and hepatitis C. Patients are managed by state of the art standard of care as well as offered opportunities to participate in clinical research as appropriate. We also have an active clinic at the UMB Drug Treatment Center (DTC) treating patients for HCV. To date, over 1240 HIV and HCV infected patients have been linked to care and over 900 patients cured of hepatitis C through treatment with novel DAA therapy within subspecialty clinics in the Baltimore and DC areas. Through direct linkage to care, effective treatment, and continual outcome

1.3 Treatment

Until recently, a major limiting factor in expansion of treatment for HCV has been standard of care therapy with pegylated interferon, ribavirin, and for genotype 1 disease, boceprevir and telaprevir. These medications have significant side effect profiles, response-based dosing regimens of over 6 months, and decreased efficacy in key groups including: those with genotype 1 disease, HIV coinfection, and cirrhosis. However, there has been dramatic improvement using all oral direct-acting antiviral (DAA) regimens with sustained virologic response (SVR) rates over 90%, short-duration therapies and well-tolerated,

simple regimens, including for those with HIV coinfection. Several studies using DAA-based therapy have shown comparable rates of sustained virologic response (SVR) in coinfected patients(14-21). In addition, data suggests that HCV eradication with use of antiviral therapy may improve cardiovascular outcomes in mono-infected patients(22). However, there is no data on the benefit of cardiovascular risk after HCV eradication in co-infected patients.

1.4 Rationale

HIV and HCV are diseases of concern in the Baltimore and DC metropolitan areas. New DAA treatments allow for effective treatment of chronic HCV and reduction in risk of extrahepatic comorbidities, including cardiovascular disease. However, no data exists on the role of HCV eradication in mitigating cardiovascular risk in HIV co-infected patients, who at baseline have an increased risk of cardiovascular disease due to the pro-inflammatory state caused by the virus and the use of ART. **This study aims to demonstrate that there is a decreased risk of cardiovascular disease after eradication of HCV in HCV mono-infected and HIV co-infected patients.** The risk factors of these patients will be compared to the risk factors for HIV mono-infected patients and HCV mono-infected patients who achieve functional HCV cure.

2 Study Objectives

2.1 Primary Objective

Determine the change in cardiovascular risk from baseline to after functional cure of hepatitis C among HCV monoinfected and HIV/HCV-coinfected patients, using high-sensitivity C-reactive protein.

2.2 Secondary Objectives

Determine the difference in change (pre vs. post functional cure) in cardiovascular risk among HCV monoinfected and HIV/HCV coinfecting patients compared to HIV monoinfected patients, using high-sensitivity C-reactive protein.

Compare the difference in levels of cardiac biomarkers between HCV monoinfected, HIV/HCV coinfecting, and HIV monoinfected patients at baseline

Determine the difference in change (pre vs. post functional cure) in cardiac biomarkers among HCV monoinfected and HIV/HCV coinfecting patients, compared to HIV monoinfected patients.

2.3 Exploratory Objectives

1. Compare the difference in cardiac MRI between HCV monoinfected, HIV/HCV coinfecting, and HIV mono-infected subjects at baseline. MRI parameters that will be assessed are the native myocardial T1, myocardial T2, and myocardial extracellular volume fraction (to look for myocardial inflammation and small

vessel disease). Gadolinium enhancement will be used to look at macroscopic fibrosis.

2. Determine the difference in change (pre vs. post functional cure) in cardiac MRI in HCV monoinfected and HIV/HCV coinfected patients, compared to HIV monoinfected patients. MRI parameters that will be assessed are listed in exploratory objective 1.
3. Determine the relationship between immune markers of activation, cardiac biomarkers, and MRI in HIV positive and negative subjects. MRI parameters that will be assessed are listed in exploratory objective 1.
4. Compare the difference in levels of cellular and soluble immune markers of activation between HCV monoinfected, HIV/HCV coinfected, and HIV monoinfected subjects at baseline.
5. Determine the difference in change (pre vs. post functional cure) in cellular and soluble immune markers of activation HCV monoinfected and HIV/HCV coinfected patients, compared to HIV moninfected patients.

3 Study Design

3.1 Description of the Study Design

This is a pilot, intervention, non-randomized, controlled prospective study. We will enroll 90 patients into the following groups. Up to 200 patients will be consented.

Group 1: HCV mono-infected patients (n = 30)

Group 2: HIV/HCV co-infected patients (n = 30)

Group 3: HIV mono-infected patients (n = 30)

Patients with HCV mono-infection (Group 1) or HIV/HCV co-infection (Group 2) will receive therapy with any FDA-approved medication for hepatitis C treatment, per standard of care in the AASLD/IDSA HCV Treatment Guidelines and/or the discretion of the investigator.

3.2 Study drugs

Direct Acting Antivirals (DAAs): For the treatment of chronic HCV, patients will be treated with one of the following FDA-approved fixed-dose combination products : Elbasvir/Grazoprevir (Zepatier), Sofosbuvir/Ledipasvir (Harvoni), Sofosbuvir/Velpatasvir (Epclusa), Glecaprevir/Pibrentasvir (Mavyret), Sofosbuvir/Velpatasvir/Voxilaprevir (Vosevi). Some of these medications require administration of concomitant ribavirin. Medication regimens will be administered as standard of care per the AASLD/IDSA HCV Treatment Guidelines. Common side effects (those that occurred in more than 5% of the patients in clinical trials) of these medications are listed below:

Elbasvir/Grazoprevir (Zepatier):

- Fatigue
- Headache

Sofosbuvir/Ledipasvir (Harvoni):

- Fatigue
- Headache
- Nausea
- Diarrhea
- Insomnia

Sofosbuvir/Velpatasvir (Epclusa):

- Headache
- Fatigue
- Nausea
- Insomnia
- Lack of energy

Glecaprevir/Pibrentasvir (Mavyret):

- Headache
- Fatigue
- Nausea
- Diarrhea

Sofosbuvir/Velpatasvir/Voxilaprevir (Vosevi):

- Headache
- Fatigue
- Diarrhea
- Nausea
- Insomnia
- Lack of energy

Ribavirin - Women of childbearing potential who receive ribavirin **must** commit to abstinence from sexual activity, or use two forms of contraception during treatment and for the 6 months after completion of ribavirin. Men receiving ribavirin who are sexually active with women **must** commit to abstinence from sexual activity, or they and their partner must use two forms of contraception during treatment and for the 6 months after completion of ribavirin. The most common side effects (occurring more than 5% of the time in clinical trials) are:

- Fatigue
- Lack of energy
- Body aches
- Fever
- Headache
- Anemia

- Rash

3.3 Research Strategy

A total of up to 200 people will be consented for the study from existing clinical sites sites and long-term natural history studies. The total N for the study is 90, HIV (n = 30), HIV/HCV (n=30), and HCV (n=30). The investigators have established clinics and networks in DC and Baltimore that have successfully recruited these patient populations for studies since 2010, including the ASCEND trial which accrued 600 patients in 10 months. Study participants will be selected based on inclusion criteria, and will be seen for study visits at clinics embedded at one of 2 sites:

- 1) Unity Healthcare, Washington, DC
 - a. An organization which serves as DC's largest network of community health centers providing comprehensive care services including primary care, HIV care, and Hepatitis B and C treatment.
- 2) Institute of Human Virology, Clinical Research Unit, Baltimore, MD

All participants HIV/HCV co-infected or HCV mono-infected patients will be treated for chronic HCV with DAAs as per standard of care (see 3.1 and 3.2.).

3.4 Primary Hypothesis

The primary hypothesis is that treatment and functional cure of HCV in HCV-monoinfected and HIV/HCV-coinfected patients should lead to decreased cardiovascular risk, as measured by at least a 2-fold decrease in high-sensitivity C-reactive protein (hsCRP) by 12 months post-functional cure of HCV.

4 Study Population

Participants are adults (age 18-70) patients infected with HIV, HCV and HIV/HCV.

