13.1 Sample Size Justification and Power

The proposal primary outcome for cardiovascular risk is change in hsCRP. The primary hypothesis is that HCV eradication will result in at least a two-fold decrease from the baseline elevated hsCRP to 12 months post-functional cure in HCV-monoinfected and HIV/HCV-coinfected patients, respectively. Based on a previous study, mean hsCRP before starting IFN-therapy in HCV-monoinfected patients was 0.97 ± 0.11 mg/L compared to 0.07 ± 0.07 mg/L in healthy controls(23). Among SVR patients the median hsCRP at baseline was 0.64 mg/L and decreased to 0.25 mg/L after treatment. With a sample size of 30 patients in each group, we assume than 95% will achieve SVR with Zepatier (elbasvir/grazoprevir), resulting in a sample size of 28 patients in each group. In a paired t-test analysis (from baseline to 12-month post-treatment), with $\alpha=0.05$, power of 90% ($1-\beta$), and standard deviation (σ) = 0.15, we will be able to detect a true difference in the mean hsCRP response of matched pairs of 0.1 mg/L in each group or 0.8 mg/L with 80% power.

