13.2 Statistical Analysis

We will perform univariate analysis to describe the demographic and clinical characteristics of the study population. Count with percentages will be calculated for categorical variables and mean + standard deviation or median (interquartile range) for continuous variables. The independent variable is the three groups of participants with HCV, HIV/HCV, and HIV. Separate analysis will be done for each study group for the change in the primary outcome of HsCRP, from baseline to 18 months after baseline, in a paired t-test analysis, as well as for the secondary outcomes of cardiac biomarkers, MRI, and cellular and soluble immune markers of activation. Baseline comparison of hsCRP, cardio biomarkers, MRI, and cellular and soluble immune markers of activation between the three groups of participants will be performed using one-way or Kruskal-Wallis analysis of variance (ANOVA) for continuous variables and chi-square test of independence or Fisher's exact test for categorical variables. A linear regression model will be used in adjusted analysis for continuous dependent variables, while logistic regression model will be used in adjusted analysis for binary dependent variables. All analysis will be conducted in SAS, version 9.4 (SAS Institute, Inc., Cary, NC) with a P-value of less than 0.05 indicating statistical significance.

14 Ethics/Protection of Human Subjects

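### The primary hypothesis is an at-least-2-fold fall in hsCRP, but the named test is a paired t-test of change, and nothing defines the fold change or what result would support it

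*Combined protocol and SAP*

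**What the plan says.** Section 3.4 sets the primary hypothesis as "at least a 2-fold decrease in high-sensitivity C-reactive protein (hsCRP) by 12 months post-functional cure of HCV". Section 13.1 repeats it, saying that eradication "will result in at least a two-fold decrease from the baseline elevated hsCRP to 12 months post-functional cure", and applies it to each HCV group.

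The objective and the aim carry no threshold. Section 2.1 reads "Determine the change in cardiovascular risk from baseline to after functional cure of hepatitis C", and section 1.4 says "This study aims to demonstrate that there is a decreased risk of cardiovascular disease after eradication of HCV".

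For the analysis, section 13.2 plans a separate test in each group of the change in hsCRP "from baseline to 18 months after baseline, in a paired t-test analysis", with P<0.05 as the only criterion. It names no log transformation, ratio, responder definition, non-zero null or confidence-interval rule, and it does not mention 2-fold. It also plans linear regression for adjusted analyses of continuous variables, but does not tie that to the hsCRP change or to a ratio. Section 13.1 sizes the paired t-test for "a true difference in the mean hsCRP response of matched pairs of 0.1 mg/L in each group", that is, for an absolute difference.

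**The concern.** The hypothesis is a statement about a ratio with a floor. The planned test asks whether a mean difference is zero. A significant result supports some fall and says nothing about whether the fall reached 2-fold.

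The term is also open. It could mean a ratio of means, a ratio of medians or a within-patient ratio, and these can differ in skewed data. With no definition or decision rule fixed in advance, P<0.05 could be reported as support for the primary hypothesis when the fall was far smaller. The ratio could also be chosen after the data are seen.

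**Working it through.** **Inputs.** From section 13.1: n=28 per group after the assumed 95% SVR in 30 patients, SD 0.15 mg/L, alpha 0.05, and a detectable difference of 0.1 mg/L at 90% power. The same section gives the historical values: "mean hsCRP before starting IFN-therapy in HCV-monoinfected patients was 0.97" mg/L, and "Among SVR patients the median hsCRP at baseline was 0.64 mg/L and decreased to 0.25 mg/L after treatment". I take the test as two-sided and 0.15 as the SD of the paired differences; neither is written out.

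**The plan's figure.** With the noncentral t on 27 degrees of freedom and a null of zero, the difference detectable with 90% power is 0.095 mg/L, which rounds to the stated 0.1. Power at exactly 0.1 mg/L is 92.5%. If 0.15 were instead the SD of each measurement, with independent measurements, the SD of the difference would be 0.15 × √2 and power at 0.1 mg/L would be only 67%. The stated figure therefore fits a test of mean change in mg/L against zero. (The 80%-power figure in the same sentence does not reproduce: I get 0.082 mg/L, not 0.8. That is a separate matter.)

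**Smallest significant fall.** Boundary = t(0.975, 27) × SD/√28 = 2.052 × 0.15/5.292 = 0.058 mg/L.
- As a share of the cited mean: 0.058/0.97 = 6%.
- A halving of that mean: 0.97/2 = 0.485 mg/L, about 8.3 times the boundary.
- The design difference of 0.1 mg/L is a 1.11-fold fall: 0.97/(0.97 − 0.10).

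**Sensitivity to the SD (values above 0.15 are assumptions).**

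| SD of difference, mg/L | Boundary, mg/L |
|---|---|
| 0.15 | 0.058 |
| 0.3 | 0.116 |
| 0.5 | 0.194 |
| 0.7 | 0.271 |
| 1.1 | 0.427 |

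The boundary reaches 0.485 mg/L only at SD = 0.485 × 5.292/2.052 = 1.25.

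**Log-scale test with n=28.** The plan gives no SD for log change, so 0.5, 0.7 and 1.0 are assumptions. Let k = exp(2.052 × SD/√28). The CI for the ratio lies below 1 once the observed geometric-mean fall exceeds k-fold. Its upper limit is at or below 0.5 once the fall reaches 2k-fold. The cited fall is 0.64/0.25 = 2.56-fold, so the shift from 2-fold on the log scale is ln(2.56/2) = 0.247.

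| SD of log change | k: fall needed for CI below 1 | Power for that at a true 2-fold fall | 2k: fall needed for upper limit ≤0.5 | Power for that at a true 2.56-fold fall |
|---|---|---|---|---|
| 0.5 | 1.21 | >99.9% | 2.43 | 71% |
| 0.7 | 1.31 | 99.9% | 2.62 | 44% |
| 1.0 | 1.47 | 94% | 2.95 | 24% |

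At a true fall of exactly 2-fold, the stricter claim is made in 2.5% of trials.

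**Why the test and the ratio should share a scale.** I simulated lognormal hsCRP with n=28, baseline median 0.64 mg/L, between-patient log SD 0.9 (assumed) and a true 2-fold fall. I then compared the mg/L t-test with the log-ratio CI on whether there was any decrease. They disagreed in about 3%, 24% and 65% of trials at log-change SDs of 0.5, 0.7 and 1.0. If baseline and week-72 log variances are equal, the figures are about 1%, 5% and 17%.

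**The case against.** The strongest reply is that 2-fold is the anticipated effect, not a threshold. Trials often state an expected effect as the hypothesis and test against zero. Section 13.1 supports that reading: it introduces 2-fold under a sample-size heading and goes on to cite a 2.56-fold historical fall. Objective 2.1 and the aim in 1.4 have no threshold, the planned test answers both, and the study is a pilot. Much of this stands. But both statements of the hypothesis set 2-fold as a minimum, and nothing says it is only an expectation.

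A reader might go further and infer that the plan has no way to tell whether its hypothesis was met. The documents do not support that. hsCRP is drawn at screening, week 24 and week 72 (section 6.4, Appendix B), so a ratio can be computed from planned data. What is missing is its definition and the rule for reading it.

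A reader might also infer that significant but trivial falls are to be expected, or that a CI in mg/L would exclude a halving in this trial. Neither follows. The 6% figure depends on SD 0.15 and on a historical baseline taken as fixed, whereas in the trial the baseline and the change come from the same patients. Nor is half the cited median (0.32 mg/L) a like-for-like comparator for a mean difference, so only half the mean is used here.

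Finally, the zero null and the mg/L scale are inferred. The reproduced power figure makes both inferences reasonable.

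**Conclusion.** The mismatch is real. The hypothesis is at least a 2-fold fall; the named test, significant or not, does not bear on it; and no section defines the fold change or the result that would support it. The planned test still addresses whether hsCRP fell.

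On the plan's inputs, significance starts at 0.058 mg/L against 0.485 mg/L for a halving of the cited mean. This shows the size of the gap and is not a forecast. It rests on SD 0.15 for the paired difference, a two-sided test, n=28 and the cited baseline taken as fixed. At an assumed SD of 1.1 the boundary is 0.43 mg/L and the gap nearly closes. That hypothesis and test ask different questions does not depend on any of these numbers.

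**What to change.** **Analysis (13.2).** In each HCV group, make the primary analysis a paired t-test on log hsCRP, week 72 against baseline. Report the geometric mean ratio with its 95% CI, so that the test and the effect are on one scale. State a simple rule for values below the assay limit, since logs need one.

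**Hypothesis (3.4 and 13.1).** State what 2-fold means, by one of two routes:
- (a) The hypothesis is a decrease, concluded if the CI for the ratio lies below 1. Give 2-fold as the anticipated effect and compare the observed ratio with 0.5 descriptively. This fits objective 2.1 and the aim in 1.4.
- (b) Keep at least 2-fold, and claim it only if the upper 95% limit of the ratio is at or below 0.5. Otherwise report the estimated fold change without claiming confirmation.

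**Cost.** No extra patients, visits or samples. The precision statement in 13.1 must be redone on the log scale with an assumed SD, which the plan does not now give. Under (a) the hypothesis is weaker and a modest fall can satisfy it (1.21-fold at an assumed log-change SD of 0.5), so the ratio and CI must be read with the test. Under (b) the claim is hard to reach with 28 patients, and the plan should state the power shown above (about 71%, 44% or 24%).
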